[figure not shown]

**Effect of a Combination of Curcuminoid Standardized Turmeric
Extract with Acupressure on Inflammatory Markers, Endorphins
and Quality of Life Elderly with Osteoarthritis Genu**

**Investigator
[name]
[name]
[name]**

**FACULTY OF MEDICINE GADJAH MADA UNIVERSITY
INDONESIA**

Table of contents

Cover	1
Table of contents	2
Protocol summary	4
1 Introduction	6
1.1 Background	6
1.2 Purpose	7
2 Study objectives and endpoints	7
2.1 Primary objective	7
2.2 Secondary objectives	7
3 Investigational plan	7
3.1 Study design	7
3.2 Study setting and source population	7
4 Population	8
4.1 Inclusion criteria	8
4.2 Exclusion criteria	8
4.3 Eligibility test procedure	8
5 Randomization, allocation and blinding	9
6 Intervention	11
7 Outcomes	12
Primary Outcomes measures	12
Secondary outcomes	12
8 Statistical Issues	13
Sample size	13
9 Protection of Human Subjects and Assessment of Safety	14
9.1 Protection of participants	14
9.2 Adverse events	14
9.3 Data analysis	14
9.4 Data management	14
10. Ethical considerations	15
10.1 Regulatory and ethical compliance	15
10.2 Informed consent procedures	15
10.3 Responsibilities of the investigator and IRB/IEC	15

10.4	Publication of study protocol and results.....	15
11.	Protocol adherence	16
11.1	Protocol amendments.....	16
12.	References	16

Protocol summary

Unique Protocol ID	KE/FK/0674/EC/2023
Title	Effect of a Combination of Curcuminoid Standardized Turmeric Extract with Acupressure on Inflammatory Markers, Endorphins and Quality of Life Elderly with Osteoarthritis Genu
Brief title	Combination of Curcuminoid With Acupressure for Inflammation and Pain in the Elderly With Osteoarthritis Genu
Sponsor and Clinical Phase	Gadjah Mada University, Phase 2a
Investigation type	Drug and acupressure
Study type	Interventional
Purpose and rationale	Evaluate the efficacy, safety and tolerability of acupressure and standardized curcuminoid from turmeric extract to inflammatory markers, endorphin hormones in the blood and quality of life in elderly patient with Osteoarthritis Genu
Primary Objective(s)	To determine the effectiveness of combination two regimens (acupressure and curcuminoid) as measured by changes from baseline (BL) in Leukocytes, Neutrophil Leukocyte Ratio, Blood Sedimentation Rate, Pain, secretion of COX-2 and Endorphin hormones in blood to placebo after 3 weeks of treatment in elderly patients with Osteoarthritis
Secondary Objectives	To evaluate the effect of acupressure and standardized curcuminoid from turmeric extract vs placebo at 3 weeks : 
 • Knee pain as measured by the VAS score • Joint stiffness and joint functional ability are assessed by the WOMAC score • The independence of the elderly as assessed by the Barthel Index • Quality of Life were measured by Respondents' satisfaction in carrying out daily activities based on indicators on the KOOS instrument
Study design	Randomized controlled trial, double-blind to assess efficacy, tolerability and safety combination of acupressure and curcuminoid versus placebo. Patients can be pre-screened for certain x-ray and laboratory parameters. Following a screening visit, eligible subjects will enter the wash-out for 1 week. After the wash-out period, eligible subjects will be randomized and treated for 3 weeks. The total duration of the study is up to 5 weeks
Population	Approximately 70 female and male patients ≥ 65 years old
Key Inclusion criteria	
 • Clinical diagnosis of osteoarthritis which confirmed by physical examination and x-rays • Experience pain with a Numeric Rating scale of 1-7 • Must be able to swallow capsules • Must be able to carry out mobility without assistance or with minimal assistance

Key Exclusion criteria	
 ● Parkinson's disease ● Dementia disease ● Psychosis disease ● New bone fractures ● Joint dislocations ● Cancer ● Rheumatic diseases other than osteoarthritis (rheumatoid arthritis) ● Undergoing joint replacement therapy. ● Analgesic dependent disease
Study treatment	
 ● Combination of Acupressure and Curcuminoid from turmeric extract ● Placebo
Efficacy assessments	
 ● Leukocytes ● Neutrophil Leukocyte Ratio ● Blood Sedimentation Rate ● Pain ● Secretion of COX-2 in blood ● Secretion of Endorphin hormones in blood
Key safety assessment	
 ● Physical examination ● Vital signs ● Monitoring of laboratory markers in blood
Others assessment	
 ● Quality of Life
Data analysis	
The primary efficacy variable is the number of Leukocytes (mCL), Neutrophil Leukocyte Ratio, Secretion of COX-2 in blood, Secretion of Endorphin hormones in blood collected at Week 4 to BL (i.e., change from BL in the number of Leukocytes at Week 4). It will be analyzed using wilcoxon signed-rank test or paired t test and Mann-Whitney U test or independent t test. The significance level will be set at 0.05. All outcome measures will be recorded at baseline and after 2 weeks of intervention

Keywords	Osteoarthritis, curcuminoid, acupressure, randomized control trial

1 Introduction

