3.1 Study design

Randomized controlled trial, we will conduct a 2-arm, double-blind (patient and investigational blinded) to assess efficacy, tolerability and safety combination of acupressure and curcuminoid versus placebo.

Pre-Screening:

Patients can be pre-screened for certain x-ray and laboratory parameters. Following a screening visit, eligible subjects will enter the wash-out. After the wash-out period, eligible subjects will be randomized and treated for 3 weeks. The total duration of the study is up to 5 weeks.

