3.2 Study setting and source population

Eligible participants were individuals recruited from communities covered by government-owned primary care hospitals who consulted a rheumatology subspecialist physician with symptoms of pain and discomfort around the knee.

Participants will be recruited from August 2023 to September 2023. An informed-consent form will be provided to participants in their local language to gain credibility. Codes will be assigned to ensure confidentiality for data collection, with only the primary researcher having access to the participant codes for each group. Participants providing their consent will be further screened for eligibility.

4 Population

The study population will consist of male and female patients (≥ 65 years old) with Osteoarthritis (Osteoarthritis with knee joint pain, knee joint stiffness in the morning less than 30 minutes, Crepitus, deformity, joint swelling (right and left asymmetrical), Other signs of inflammation (a feeling of even warmth and reddish color). The goal is to randomize a total of approximately 70 patients. Since a 25% screening failure rate and a 20% washout failure rate is expected, approximately 100 patients will be screened.

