4.1 Inclusion criteria

Patients eligible for inclusion in this study must fulfill all of the following criteria:

1. Clinical diagnosis of osteoarthritis which confirmed by physical examination and x-rays
2. Experience pain with a Numeric Rating scale of 1-7
3. Must be able to swallow capsules
4. Must be able to carry out mobility without assistance or with minimal assistance

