4.3 Eligibility test procedure

Radiographs will be used to assess participants for Osteoarthritis using the Kellgren and Lawrence criteria which divide Osteoarthritis from mild to severe. It should be remembered that at the beginning of the disease, the radiographic appearance of the joint still looks normal. According to Kellgren and Lawrence, radiologically, osteoarthritis is classified as follows:

- 1) Grade 0: Normal, no signs of osteoarthritis
- 2) Grade 1: Doubtful, without osteophytes, doubtful joint narrowing

3) Grade 2: Minimal, few osteophytes on the tibia and patella and the joint surface is asymmetrically narrowed.

4) Grade 3: Moderate, there are moderate osteophytes in several places, the joint surface is narrowed, and subchondral sclerosis appears.

5) Grade 4: Severe, presence of large osteophytes, complete narrowing of the joint surface, severe subchondral sclerosis, and joint surface damage.

Mini Mental State Examination (MMSE) test will be used to assess the patient's cognitive abilities. This is important to ensure that patients can understand the instructions in the treatment process and the outcome measurement process.

5 Randomization, allocation and blinding

A total of 70 eligible participants will be randomized to the group with curcuminoids capsules and acupressure (C+A; group 1) or the group with placebo and sham acupressure (P+S; group 2) via lottery randomization. Thereafter subjects will be randomly allocated to C+A and P+S group. The schematic CONSORT (Consolidated Standards of Reporting Trials) flow diagram for the study protocol is presented in Figure 1. Schematic CONSORT (Consolidated Standards of Reporting Trials) flowchart for the study.

[figure not shown]

Figure 1. Schematic CONSORT (Consolidated Standards of Reporting Trials) flowchart for the study

Determination of baseline characteristics for every participant will be done by the therapist through a standardized assessment form. During the baseline measurement, the following characteristics will be recorded: sex, age, body mass, pain characteristic, history of disease and medication use. The participant's participation schedule will be determined according to the SPIRIT (Standard Protocol Items: Recommendations for Interventional Trials) statement Figure 2. The primary and secondary outcome measures will be recorded before providing the intervention.

[figure not shown]
TIMEPOINT**	STUDY PERIOD								
	Enrolment	Allocation	Post-allocation			Close-out			

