		0	1 st week	2 nd week	3 rd week	1 st day	1 st week	2 nd week	Post 3 rd week
ENROLMENT:									
Eligibility screen	X								
Informed consent	X								
[Radiography and MMSE Test]	X								
Allocation		X							
INTERVENTIONS:									
[C+A Therapy]			X	X	X				
[P+S Therapy]			X	X	X				
ASSESSMENTS:									
[Demographic Details]	X								
[Inflammatory Marker]						X			X
[Endorphine]						X			X
[Quality of Life]						X	X	X	X

Figure 2. SPIRIT (Standard Protocol Items: Recommendations for Interventional Trials) recommended schedule for participation.

6 Intervention

After the standardized assessments and baseline measurements, the intervention will be conducted. Participants will be randomly assigned to the CA group or the PS group. For Acupressure Therapy and Sham Acupressure, each participant will be exposed to 3 therapy sessions per week of 20 minutes for 3 consecutive weeks. Participants will not be allowed to take any medication routinely during this time except for antihypertensive agents, thyroid medications, and antidiabetic drugs. To help participants adhere to the interventions, reminder messages will be sent before each session visit. For Curcuminoid capsules and placebo, Each participant will be exposed to taking capsules three times a day for 21 days.

Acupressure to perform CA, the patient is put in the supine position with legs straight. Prepare tools and materials such as a seat (or bed), warm water, olive oil, wet & dry tissue, towels. The therapist washes his hands, the client sits in a comfortable position. Teach patients breathing relaxation techniques to use during therapy. Give patients the opportunity to pray according to their respective beliefs. Make sure the client is relaxed and comfortable. Help remove the client's clothing or accessories that may hinder the acupressure action being performed, if necessary. Perform a client pain assessment. Wipe the client on the parts to be massaged with warm water that has been treated with a disinfectant solution using a small towel. Dry with a clean towel. Use cream or oil, do a warming massage with basic massage techniques, choose according to the client's condition (rubbing, squeezing, pressing) and stretching the patient's feet. Acupressure massage points are performed at ST34, ST36, Tai Xi Acupoint, GB34, SP 9, SP 8, EX-LE, EX-LE3, EX-LE4, EX-LE6, EX-LE7, EX-LE10

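### Medication use is recorded only at baseline, so analgesics taken during the 3 weeks would go unseen; the protocol also leaves unstated when the 1-7 pain criterion is scored relative to the wash-out

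*Combined protocol and SAP*

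**What the plan says.** **Medication.** Section 5 describes the baseline assessment: "the following characteristics will be recorded: sex, age, body mass, pain characteristic, history of disease and medication use". Section 6 sets the rule for the treatment period: "Participants will not be allowed to take any medication routinely during this time". It exempts antihypertensive, thyroid and antidiabetic medicines, and does not mention analgesics taken now and then. Figure 2 has rows for demographic details, inflammatory markers, endorphin and quality of life, but none for medication. Section 7 (outcomes), Section 9.2 (adverse events) and Section 9.3 (data analysis) do not mention medicines taken after baseline. Section 11 forbids investigators from gathering further data for research purposes; the allowance it makes is for assessments needed for patient safety, case by case.

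**Wash-out and pain criterion.** The Protocol summary places a one-week wash-out after screening: "Following a screening visit, eligible subjects will enter the wash-out for 1 week". Section 3.1 continues: "After the wash-out period, eligible subjects will be randomized and treated for 3 weeks". The inclusion criterion in Section 4.1 reads "Experience pain with a Numeric Rating scale of 1-7" and carries no time point. Section 4 states: "Since a 25% screening failure rate and a 20% washout failure rate is expected, approximately 100 patients will be screened"; the aim is to randomise about 70. In Figure 2 the row "Eligibility screen" has one cross, under Enrolment, and the schedule has no wash-out column.

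**The concern.** The trial compares active treatment with placebo and sham on pain and inflammatory markers over 3 weeks, in patients who have stopped or restricted other treatment. Some are likely to take a painkiller on a bad day, and the rule in Section 6 does not clearly forbid it. The Background names NSAIDs as the most common drug treatment for this pain. It also cites a trial in which curcuminoids did not differ significantly from diclofenac in their effect on COX-2 secretion, leukocytes and pain. That trial studied synovial fluid rather than blood, and a non-significant difference does not establish equal effect. Even so, the protocol's own evidence suggests that an NSAID acts on the same kinds of outcome as the test product.

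If placebo patients use more analgesics, the arm difference shrinks; if active patients use more, it grows. Without a record nobody could say which happened, or whether anything did. Dates and times of use could not be recovered reliably after the trial.

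The second matter is one of definition. If sites differ on whether the pain range must still hold after wash-out, the randomised population is not uniquely defined, and nor is the group to be counted as wash-out failures.

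**Working it through.** **1. Where medication is captured.** Reading through the trial in order:

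- Baseline (Section 5): medication use recorded.
- Nine sessions (Section 6; 3 per week x 3 weeks = 9): a pain assessment and a request to report discomfort, but no medication item.
- 3-week assessment (Section 7, Figure 2): outcomes only.
- Analysis (Section 9.3): no mention.

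The only record precedes the period in which use would matter.

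**2. Illustration on pain.** The documents give no rate of analgesic use and no effect of an analgesic on these outcomes, so every input here is assumed: a true difference of 1.5 points, and an analgesic that lowers the final score by 2 points. With proportions p of users in each arm, shift = 2 x (p_placebo - p_active).

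| Placebo use | Active use | Shift | Observed difference | Change |
|---|---|---|---|---|
| 20% | 10% | 0.20 | 1.3 | 13% loss |
| 30% | 10% | 0.40 | 1.1 | 27% loss |
| 40% | 10% | 0.60 | 0.9 | 40% loss |
| 10% | 10% | 0 | 1.5 | none |
| 10% | 20% | -0.20 | 1.7 | 13% gain |

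Unequal use between arms drives the result, and it can act in either direction.

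**3. Illustration on power.** The plan's figure first, with the Section 8 inputs (SD 14.01; difference 174.27 - 164.1 = 10.17; z values 1.96 and 0.842):

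N = 2 x 14.01² x 2.802² / 10.17² = 3082.07 / 103.4289 = 29.80, rounded up to 30. This reproduces the plan, which uses it as the number per group.

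Now assume that unrecorded use removes a share s of the difference. Power = Φ[10.17(1 - s) / (14.01 x √(2/n)) - 1.96].

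| s | n = 30 per group | n = 35 per group |
|---|---|---|
| 0% | 80% | 86% |
| 10% | 72% | 78% |
| 20% | 61% | 68% |
| 30% | 50% | 57% |

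The shares s are assumptions. The difference and SD are taken from Section 8 as they stand, without endorsement.

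**4. Screening count.** Inputs from Section 4: 100 screened, 25% screening failure, 20% wash-out failure, target 70.

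- Applied in sequence: 100 x 0.75 x 0.80 = 60, which is 10 short of 70.
- Number needed in sequence: 70 / (0.75 x 0.80) = 116.7, so 117.
- Both rates taken from those screened: 70 / 0.55 = 127.3, so 128.
- Adding 45% to the target: 70 x 1.45 = 101.5. This comes near 100, but it applies the failure rates to the wrong base.

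**5. When the pain criterion applies.** Section 4.1 gives a range without a time. The Protocol summary calls patients eligible both before wash-out and at randomisation. Section 4 expects failures at wash-out but does not define them. Figure 2 cannot settle the order because it shows no wash-out. Baseline outcomes, including pain on a VAS, are recorded before treatment, but no text ties that score to the NRS range.

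**The case against.** Several points weigh on the other side.

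- *The rule and the exclusions already limit analgesics.* Section 6 restricts routine medication, and exclusion 9 removes disease that depends on analgesics. Both help, but neither reaches the occasional user, and neither says how adherence would be checked.
- *The illustrations show nothing about this trial.* This stands. All usage rates and effects are assumed, and no effect on leukocytes, the neutrophil ratio, COX-2 or endorphin can be estimated. The pain example also concerns an outcome that Section 7 lists as secondary, although Section 2.1 includes it in the primary objective. The tables show the mechanism and its direction only.
- *A comparison of all randomised patients remains valid whatever they take.* As a comparison of assigned strategies, this is right. What is lost is the ability to attribute the difference, or its absence, to the combination itself.
- *The pain range is checked only before wash-out.* A reader might infer this, and might go on to conclude that a patient whose pain rises above 7 off medication is still randomised. The documents do not support that. The criterion has no time point, eligibility is mentioned again at randomisation, and an expected wash-out failure rate implies some check. Figure 1, the CONSORT flowchart, was not available to this review and may show one. Nor do the documents give a reason for the 1-7 range, so no claim about whom it protects can rest on them.

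**Conclusion.** The medication gap is real. Medication use is recorded at baseline only, occasional use is not addressed, and Section 11 prevents sites from filling the gap informally. Analgesic or anti-inflammatory use during the 3 weeks would be unseen and could not be analysed. The size and direction of any bias are unknown. The figures of 13% to 40% loss, and the fall in power from 80% to as low as 50% at 30 per group, depend wholly on assumed inputs. The gap does not invalidate the trial, but it is cheap to close beforehand and cannot be closed reliably afterwards.

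On the pain criterion the conclusion is narrower. The protocol does not say when the NRS range is scored relative to wash-out, or what a wash-out failure is. Randomisation outside the range is possible, not shown. The screening count is inconsistent with the plan's own failure rates: 60 rather than 70 when they are applied in sequence.

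**What to change.** **Medication record.** By protocol amendment, add one fixed question on the drug, date and time of the last analgesic or anti-inflammatory taken. Ask it at baseline, at each of the nine existing sessions and at the 3-week assessment, in the same words in both arms, and add a row to Figure 2.

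**Analysis.** In Section 9.3, state that use will be reported by arm and that all randomised patients stay in the main analysis. Pre-specify one sensitivity analysis for use shortly before the final measurement, with the window fixed before unblinding. It should not simply drop users, because use occurs after randomisation and excluding on it can itself bias the comparison. One suitable form shifts users' final values by a stated range of amounts and reports where the conclusion changes.

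**Reconciliation.** The Protocol summary, Sections 3.1, 4, 4.1 and 6, and Figure 2 must be made to agree on when the NRS criterion is scored, what counts as a wash-out failure, and how as-needed medication is treated. The screening number must be made to match the stated failure rates. Which clinical rule applies is for the investigators; none is proposed here.

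**Cost.** One extra form item and a few minutes per visit: 11 short entries per patient (1 + 9 + 1), or 770 for 70 patients, all at contacts already planned. If the failure rates are kept, reconciling the count may mean screening more than 100 within the August to September 2023 recruitment window. That shortfall is already in the plan and does not come from the medication question.

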2.1 Primary objective

To determine the effectiveness of combination two regimens (acupressure and curcuminoid) as measured by changes from baseline (BL) in Leukocytes, Neutrophil Leukocyte Ratio, Blood Sedimentation Rate, Pain, secretion of COX-2 and Endorphin hormones in blood to placebo after 3 weeks of treatment in elderly patients with Osteoarthritis

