The patient is observed for a local twitch response. The patient is asked to report any abnormal sensations or discomfort during the course of intervention.

The sponsor will provide double-blind study medication for Curcuminoid and Placebo

Preparation of standardized curcuminoid turmeric extract preparations. Samples were made from extracted turmeric and then optimized. The capsule formulation is made from turmeric rhizome extract which contains 30 mg of curcuminoids per capsule. In the study, standardized curcuminoid turmeric extract was given in capsules at a concentration of 30 mg 3 times a day for 3 weeks.

7 Outcomes

All outcome measures will be assessed at baseline and after 3 weeks of intervention.

Primary Outcomes measures

1) Inflammatory Markers

Inflammation markers are carried out by measuring leukocyte numbers and the Neutrophil Lymphocyte Ratio. The examination is carried out using a complete blood test using a Hematology Analyzer, which is a laboratory tool used to measure and count the number of blood cells. The blood samples are mixed using a mixture of reagents to create a process called hemolyzing. This process will be divided into several purposes, to measure leukocytes, neutrophils, platelets and erythrocytes.

2) Secretion of the COX-2 hormone

The enzyme cyclooxygenase-2 (COX-2) is an important mediator in increasing the inflammatory response. In the blood plasma of patients with osteoarthritis, the COX-2 enzyme can be detected. The COX-2 hormone examination was carried out using the Enzyme Linked Immunosorbent Assay (ELISA) method on blood plasma.

3) Secretion of endorphin hormones

Endorphins, in this case beta endorphin, are hormones released by the pituitary gland in response to stress or pain, which are also secreted in blood plasma. Endorphin hormone levels in the blood were measured before starting therapy and after 3 weeks of therapy.

Endorphin hormone examination is carried out using the Enzyme Linked Immunosorbent Assay (ELISA) method on blood plasma that has been incubated at room temperature for 10-20 minutes, then the tube will be centrifuged for 20 minutes at a speed of 2000-3000 rpm.

Secondary outcomes

The effectiveness of therapy is the ability of the therapy regimen given to suppress several other expected output indicators. Other output indicators were measured before starting therapy and after 3 weeks of therapy

1) Knee pain as measured by the VAS score

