9.3 Data analysis

The data collected will be analyzed by the secondary researcher. Descriptive statistics will be used to evaluate the baseline characteristics of participants. The normality of the collected data will be established using the Shapiro–Wilk test. Based on data normality, descriptive statistics will be expressed as mean \pm standard deviation or median (interquartile range). Within-group comparisons will be conducted using the Wilcoxon signed-rank test or a paired t test. Similarly, the Mann–Whitney U test or an independent t test will be used for between-groups comparisons. The level of significance will be set at 0.05.

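### The primary endpoint is six variables in the objective and four in the analysis, each tested at 0.05 with no rule for success, so the chance of a false positive can reach 18.5% (four) or 26.5% (six)

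*Combined protocol and SAP*

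**What the plan says.** **Primary list.** The primary objective in the Protocol summary measures effectiveness by "changes from baseline (BL) in Leukocytes, Neutrophil Leukocyte Ratio, Blood Sedimentation Rate, Pain, secretion of COX-2 and Endorphin hormones in blood to placebo", and Section 2.1 repeats these six variables. The summary's Data analysis row gives four: "The primary efficacy variable is the number of Leukocytes (mCL), Neutrophil Leukocyte Ratio, Secretion of COX-2 in blood, Secretion of Endorphin hormones in blood". Section 7 has three primary headings that hold the same four variables.

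**Pain and sedimentation rate.** Pain is in the six-variable objective, yet the summary's secondary objectives and the secondary outcomes in Section 7 both list "Knee pain as measured by the VAS score". Sedimentation rate has no entry in Section 7.

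**Neutrophil ratio.** The objective and the summary analysis divide neutrophils by leukocytes. Section 7 divides by lymphocytes: "Inflammation markers are carried out by measuring leukocyte numbers and the Neutrophil Lymphocyte Ratio".

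**Tests.** The summary states "It will be analyzed using wilcoxon signed-rank test or paired t test and Mann-Whitney U test or independent t test". Section 9.3 states "Within-group comparisons will be conducted using the Wilcoxon signed-rank test or a paired t test", adds a between-group test, and ends with "The level of significance will be set at 0.05". Neither place ranks the variables or the two kinds of test, adjusts the level, or says what counts as a positive trial.

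**The concern.** The stated aim is to determine effectiveness against placebo, but the plan does not say what result would show it. A significant result on any one marker from either list could be presented as a positive primary finding. So could a before-after change within the treated arm, which is not evidence against placebo because both arms may change alike. As the plan stands, the list, the definition of the ratio, the comparison and the number of successes required could all be settled after the results are known. Careful reporting afterwards cannot repair that.

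**Working it through.** **1. The plan's own figure.** Section 8 sizes the trial on leukocytes alone: difference 174.27 − 164.1 = 10.17, SD 14.01, z-values 1.96 and 0.842.

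N = 2 × 14.01² × (1.96 + 0.842)² / 10.17² = 29.8, so 30 per group. This reproduces. It is a calculation for one variable at an unadjusted two-sided 0.05, with no allowance for several primary variables.

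**2. Family-wise error, between-group tests.** Suppose there is no true effect on any variable and any one significant result counts.

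- Independent, either direction: 1 − 0.95^4 = 0.1855; 1 − 0.95^6 = 0.2649.
- Independent, favourable direction only: 1 − 0.975^4 = 0.0963; 1 − 0.975^6 = 0.1409.

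The documents give no correlations, so equal correlations of 0.5 and 0.9 are assumed to show the range (simulated normal test statistics):

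| Variables | Correlation | Either direction | Favourable only |
|---|---|---|---|
| 4 | 0 | 18.5% | 9.6% |
| 4 | 0.5 | 15.6% | 7.8% |
| 4 | 0.9 | 9.3% | 4.7% |
| 6 | 0 | 26.5% | 14.1% |
| 6 | 0.5 | 20.7% | 10.4% |
| 6 | 0.9 | 10.8% | 5.5% |

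The reference rates for one test are 5% (either direction) and 2.5% (favourable only). Every row exceeds its reference.

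**3. If a significant change within the treated arm also counts.** With no true change in either arm, either direction, the rates for four / six variables are 29.4% / 40.6% when independent and 24.7% / 32.2% at correlation 0.5. Favourable direction only, independent, they are about 15.7% / 22.5%.

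**4. If every variable had to succeed,** the rate would be at most 5%. No section says so.

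**5. Price of adjusting.** Holm's first step with four variables is 0.05/4 = 0.0125. On the plan's inputs (10.17, SD 14.01, 30 per group), t-test power is 0.789 at 0.05 and 0.594 at 0.0125 (normal approximation 0.803 and 0.623). Power of 80% at 0.0125 needs 44 per group (43 by the normal approximation).

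**6. The SD behind those powers.** (78.93 − 50.91)/2 = 14.01, so the SD used is half the difference of the two spreads quoted in Section 8. If those spreads are group SDs (Section 8 does not label them), the pooled value is √((50.91² + 78.93²)/2) = 66.4. Leukocyte power at 35 per arm is then 0.097 at 0.05.

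**7. Related wording.**

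- *Time of assessment.* The summary's Data analysis row records outcomes after 2 weeks of intervention. Sections 2.1 and 7 say 3 weeks, and the Figure 2 schedule takes inflammatory markers and endorphin only on the 1st day and post 3rd week.
- *Week 4.* The same row uses this label without saying when counting starts. Counted from the 1-week wash-out, it may be the end of treatment.
- *Sidedness.* Section 8 calls the hypothesis unidirectional but uses 1.96, the two-sided 0.05 value.

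**The case against.** The strongest reply is that the plan does point to a lead variable and a lead comparison. The summary speaks of the primary variable in the singular, illustrates it with the change in leukocytes, and Section 8 is sized on leukocytes. The objective is worded as a comparison with placebo after 3 weeks, so a before-after change in one arm would not meet it. These are hints, not designations. The sentence that illustrates with leukocytes itself lists four variables, the objective lists six, and the analysis text lists within-group tests without calling them descriptive. The treated-arm rates do rest on the looser reading and should be seen that way.

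It is also fair that a significant worsening could not be claimed as effectiveness, and that leukocytes and the neutrophil ratio come from the same blood count. Favourable-only and correlated figures are therefore more relevant to a false claim of benefit. They are about half the headline or lower, yet still above 2.5%.

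The trial is Phase 2a, where strict family-wise control over biomarkers is partly a matter of judgement. That may bear on the choice of remedy, but it does not excuse two primary lists. The requirement for approved amendments (Section 11.1) and public posting of key design elements (Section 10.4) restrict later changes, but neither says which of the conflicting lists applies.

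Two cautions on the costing stand. The power figures for adjustment carry leukocyte inputs over to markers for which the documents give no effect or SD, and those inputs include the doubtful 14.01. Also, 1.96 would fit a one-sided 0.025 test as well as a two-sided 0.05 test.

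**Conclusion.** The concern holds and must be fixed. The documents contradict themselves on what is primary, and the tests are neither ranked nor adjusted. If any one significant between-group result counts, the family-wise error is 18.5% (four variables) or 26.5% (six), assuming independence and no true effect. Over assumed correlations up to 0.9 it falls as low as 9.3% or 10.8%, and for favourable results only it runs from 9.6% / 14.1% down to 4.7% / 5.5%. The size depends on the unstated success rule and correlations. The contradiction in the lists depends on no assumption.

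**What to change.** Put one primary list in the summary objective, the summary analysis, Section 2.1 and Section 7, with one denominator for the neutrophil ratio. Then choose one of two routes.

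- **A.** Name one primary variable and make the others secondary, including sedimentation rate and VAS pain, each with an entry in Section 7. Leukocytes is a candidate because Section 8 uses it.
- **B.** Keep the four Section 7 markers and control the overall two-sided error at 0.05 with Holm.

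Under either route, add: *Success rests on the between-group comparison of change from baseline to the post-3rd-week assessment; within-group tests are descriptive.* Reconcile the 2-week line in the summary with Sections 2.1 and 7 and the schedule, state from when Week 4 is counted, and describe the hypothesis as two-sided to match 1.96.

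**Cost.** Text changes in the summary and Sections 2.1, 7 and 9.3, and a redone Section 8. Under A, fewer markers can carry a primary claim. Under B, per-marker power at Holm's first step falls from about 80% to about 60% at 30 per group on the plan's inputs, and 43 to 44 evaluable per group would be needed to restore 80%. Because the SD of 14.01 is itself in doubt, power must be restated whichever variable is chosen.
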